We acknowledge that our sample sizes will be small given the low incidence of PKAN in the general population. Thus, our focus will be on estimating the magnitude of effects to capture disease progression and reaction to intervention. We will explore correction techniques for small sample size, such as bootstrapping, shown to work with similar models with small sample sizes (e.g., $N = 33$), as well as Bayesian analyses. We will handle missing data with full information maximum likelihood estimation, which will lessen the risk of bias and loss of power due to missing data.

Data analysis

Our clinical experience with PKAN has informed our approach. We expect to observe differences from one subject to another in their initial functional status and in the rate of change in functional status after intervention. Furthermore, we know that children with PKAN will first gain and then lose function over time. The use of LGC models allows for both variable-centered and subject-centered elements in the analysis. This is critical given our prediction that subjects will demonstrate different patterns of disease progression and may have individual differences in responding to treatment. Our modeling strategy does not rely on an assumption of uniformity in progression rate or treatment effects and allows for flexible multivariate growth curve models to be constructed, allowing us to capture subtleties in disease progression and influences (e.g., a disease-modifying intervention) on it that might be masked by traditional analyses. This approach will allow us to examine change at the group level while modeling individual differences in initial functional status and change in function over time. We will be able to examine trajectories of motor, cognitive, social, language and adaptive functioning to track developmental milestone attainment and loss and determine if these are linear or non-linear. We will be able to determine whether a putative disease-modifying agent alters the natural history of the disease. In addition, we will assess the sensitivity of individual measures (e.g., upper extremity function score) compared to a combination of measures (e.g., global mobility score) to detect change. This will inform refinement of models and measures to

capture accurately fast vs slow disease progression monitoring and responses to intervention levels.

Constructing the model

We will use the Mplus software (v.8) to estimate LGCs including robust standard errors and corrected chi-square values to handle non-normality and missing data as needed. The model parameters of interest will be the overall level of skill or ability (i.e., intercept) and amount of change (i.e., slope) for the domain assessed. The basic model, a starting point, is defined as:

$$Y_{it} = \alpha_{yi} + \beta_{yi}\lambda_t + \epsilon_{it},$$

where Y_{it} is assumed to represent the repeated measures (motor domain), where i stands for a person, t represents the time-ordered measurements, α_{yi} is defined as the initial functioning status on a given domain for a person's trajectory and β_{yi} is the slope representing change. In addition, λ_t represents the measured time points and ϵ_{it} represents the residual for each person. This base model allows one to develop more complex models of linear or non-linear trajectories, including covariates (e.g., age, mutation, intervention). Several indices will be used to evaluate model fit, including indices such as: chi-square (χ^2), Comparative Fit Index (CFI), and the Standardized Root Mean Squared Residual (SRMR). For example, a CFI value greater than or equal to 0.95 with a SRMR value at or below 0.05 indicate excellent fit.

Three broad steps will define model building and trimming. First, trajectories of the domains of interest will be examined in unconditional LGCs. We will explore both linear and non-linear models to determine what best captures change and compare these models statistically for best fit. Next, we will combine the single models into a multivariate unconditional model across domains where the parameter estimates are obtained controlling for other variables in the model. For example, the estimates of baseline status of cognitive functioning in the unconditional multivariate model will control for the baseline levels of the motor functioning. This will allow for the correlation between the initial levels of functioning and change in these in functioning to be estimated, enabling us to understand the shape and level of change. Finally, we will add covariates (e.g., intervention group) to models. It is the conditional multivariate LGC where the influence of - or differences due to - these covariates on initial status and rates of disease progress can be estimated. We will also use recent work in this area to enable re-parameterization of such models to make the results more meaningful in terms of the parameter estimates reflecting quantities of interest to daily functioning. This modeling process will allow us to trace the disease progression over various patient functioning variables, the influence of the intervention on the change trajectory, and begin to understand how disease progression of PKAN occurs at the aggregate and individual level. The product of this effort will be a robust model and parameter estimates of the natural history of PKAN with key outcomes that can inform the variability in the intervention effects while controlling for other variables. Model estimates will be essential for the planning of larger scale studies of compounds with putative disease-modification effects such as 4'-PPT.

d. Other analyses

Adherence and retention analyses

Adherence will be defined as the proportion of product consumed in each study time period, averaged over all periods with weighting to compensate for uneven spacing of collection points.

eIRB 18782 CoA-Z in PKAN (NIH)

Subjects will be instructed to return all unused study product to the site at the end of each study time period, with pre-paid mailers provided along with blood draw supplies and the next time period's study product supply. Adherence to the study product regimen will be assessed by calculating actual product consumed / expected product consumption. In the event that the unused portion is lost, the study team will ask the participant to approximate. We will compare means and standard deviations among the four study arms during the first six months and among the three dose groups in the Primary Cohort in months 7-36.

Retention will be tabulated as the number participating at the end of each month from baseline to month 37 (including the final follow up visit), grouped by study arm and annotated with reason(s) for study exit. Exit may occur if the participant is lost to follow up or indicates that s/he is no longer willing or able to participate.

Baseline descriptive statistics

Intervention groups (4 groups of 15 participants each) and the direct to open-enrollment group will be compared on baseline characteristics, including PKAN type, age, gender, laboratory measurements, and CoASY mRNA expression levels using descriptive statistics. Inferential statistics will not be used.

Additional sub-group analyses

Age will be evaluated as a covariate in secondary analyses.

Tabulation of individual response data

Safety and tolerability events will be listed for individual participants by measure and time point. Individual CoASY expression profiles over time will be plotted for visual inspection.

e. Procedures to minimize bias

Measures to minimize bias

Randomization/masking procedures

Study statisticians will prepare randomization lists stratified by PKAN type and deliver these to the research pharmacy. The study team will remain blinded to treatment assignment throughout the study. The Independent Medical Monitor can instruct the Research Pharmacy to break the blind for a given subject if deemed medically necessary, or under conditions outlined in the DSMP. The research pharmacy will distribute the randomization scheme for data analysis purposes following standard procedures.

Evaluation of the success of blinding

We will assess the success of blinding in at six months, before unblinding, by asking participants or their proxies to which treatment allocation they think they were assigned. Possible responses will fall in five categories of "Strongly believe the treatment is active", "Somewhat believe the treatment is active", "Somewhat believe the treatment is placebo", "Strongly believe the treatment is placebo" and "Don't know." We will calculate and compare blinding

eIRB 18782 CoA-Z in PKAN (NIH)

indices (BI) in each arm using the method of Bang et al. We will not use statistical inference testing because of the limited size of the study.

11. Privacy, Confidentiality, and Data Security

As noted, most participants will be recruited from those in our established repository (eIRB 7232) and our PKAN natural history study (eIRB 10832). Only participants who have already provided consent to be re-contacted about future research opportunities will be contacted. Other potential subjects may contact our team after seeing an IRB-approved post about the study on our website, via clinicaltrials.gov, or other means. When any potential participants are reached by phone, if they feel they do not have sufficient privacy, study staff will offer to call them back at a better time. Study staff will not leave any sensitive information in messages left on voicemail.

Consent phone calls will be pre-arranged at a designated time when potential participants can ensure their privacy. Following the consent discussion, a secure link to the online consent form in REDCap Cloud will be sent via the OHSU email system. Rarely, a paper consent form will instead be mailed for signatures with a return envelope. Participants being seen at OHSU for clinical care will be consented face-to-face in a private exam room at OHSU.

All study visits will be done remotely by phone. Again, if a participant feels they do not have sufficient privacy, study staff can offer to call them back at a later time that day. Safety labs and research blood samples will be collected by a designated lab local to each subject. In most cases, samples will be collected at Quest clinical draw stations that meet standard privacy requirements. A small number of participants in more remote locations may have blood collected at their local physician's clinical offices, which should provide a similar level of privacy.

Blood samples sent to OHSU for research biomarker testing will be received by study staff and re-labeled with a code number that does not contain any part of the 18 HIPAA identifiers. Study staff will generate a key to the codes that will be maintained by the study coordinator. This key will be restricted to the PI and study staff and will be kept secure on a restricted OHSU network drive in a limited access folder. [name] Lab staff will only have access to subject code numbers and will not be able to link back to names or other identifiers. Samples will be stored in the [name] lab freezer. The lab requires badge-access and is only accessible to those with permission. Samples will be stored until the study is complete. At that point, leftover samples will be transferred into the associated research repository established for this purpose and stored indefinitely.

Study data will be entered and stored electronically in a 21 CFR Part 11-compliant REDCap Cloud database, a web-hosted application hosted by nPhase (located in Encinitas, CA), an approved system that has been reviewed by OHSU security. Electronic files of safety lab data will be downloaded from Quest Diagnostics's secure portal periodically onto a secure OHSU server as a CSV or Excel file for upload to our REDCap Cloud database. Paper copies of safety labs and/or study product dose logs completed by subjects faxed or sent to the study site will be stored in a locked filing cabinet in an office that requires badge access. Upon receipt, standard institutional practices will be followed as described in the OHSU Information Security and Research Data Resource Guide to maintain the confidentiality and security of the data collected in this study. Study staff will be trained with regard to these procedures.

12. Provisions to Monitor the Data to Ensure the Safety of Subjects

See also separate Data Safety Monitoring Plan document. This study will have multiple levels of monitoring, including investigator-monitors, a medical safety monitor, and a full Data Safety Monitoring Board.

The neurologist PI ([name]) and pediatrician-medical geneticist Co-I ([name]) who will act as real-time investigator-monitors in this clinical trial each have many years of experience conducting clinical studies in the vulnerable populations involved in the study. Their clinical and research careers have been dedicated to children and adults affected with inherited diseases. [name], a medical geneticist with extensive research and clinical experience in the management of children and adults with genetic and metabolic diseases, will serve as the independent medical safety monitor for this study. [name] will also serve as Chair of the Data Safety and Monitoring Board that will be convened prior to the start of the study, and which will meet on a scheduled and, if needed, *ad hoc* basis to review summary reports of the study progress and any adverse events that have occurred and will make formal recommendations based on these data as to whether to suspend, terminate or continue the research. The study team will follow OHSU's policy and procedures for inclusion of decisionally-impaired adults at: (<http://www.ohsu.edu/xd/about/services/integrity/policies/upload/di.pdf>).

The PI will review all adverse events in real-time, taking immediate action as needed in consultation with the clinical Co-I and Medical Safety Monitor. In addition, the PI will make a formal determination of seriousness and relatedness for each adverse event for data recording purposes and to meet reporting requirements, again consulting with the Medical Safety Monitor as needed.

13. Risks and Benefits

a. Risks to Subjects

Because it has not been studied in humans before, the study product poses unknown risks. However, our expectation is that toxicity will be very low for this high-purity compound that is identical to a naturally-occurring product of intermediary metabolism; which has shown no toxicity at all at high doses in mouse studies completed to date; and which is being dosed at "minimum effective" rather than the more usual "maximum tolerated" doses. The "minimum effective" dose derived from mouse studies turns out to be remarkably close to the molar equivalent of the recommended daily allowance (RDA) of the source vitamin pantothenate, which itself shows little toxicity even in doses far in excess of the RDA^[9]. The dose to be used in this study is within usual dietary intake ranges of the parent vitamin, pantothenate.

All clinical procedures involved in this research (blood draws) are judged to pose minimal risk to even the youngest of participants. There also exists a small risk of loss of confidentiality of the data collected; these data may include sensitive genetic information.

b. Potential Benefits to Subjects

Although the aims of this study are to examine safety, tolerability, and pharmacodynamic response of a vitamin metabolite for PKAN, the nutritional management of the disease with the study product may afford clinical benefits for participants over the study participation period.

c. Importance of Knowledge to be Gained

If the study product is found to be safe and well-tolerated and exploratory pharmacodynamic measures provide “proof of concept” for its use for the nutritional management of PKAN, the product will offer an alternative to drugs in development that may carry higher risks of toxicity and be less palatable. While we of course hope that the proposed exploratory analysis will demonstrate a beneficial effect on disease progression, we suspect that this may require that the food be initiated early in disease, before substantial neurodegeneration has already taken place.

We hope that our novel remote trial design, if successfully executed, will provide the impetus to consider a similar approach for future studies in this and other disease populations, especially where the interventions are low risk and the barriers to research participation and disease burden are high.

Any drug alternative is likely to be much more expensive to patients, families and insurance companies than this medical food, which is being developed by sister non-profit organizations in the US and Netherlands committed to keeping the cost as low as possible to enable universal access to all families regardless of health insurance coverage or financial resources. We hope this non-profit approach will serve as a model for therapeutics development in other disorders and ultimately promote equitable access to potentially life-saving interventions.

References

1. [name], S. J., Westaway, S. K., Levinson, B., Zhou, B., Johnson, M. A., Ching, K. H., & Gitschier, J. (2003). Genetic, clinical, and radiographic delineation of Hallervorden-Spatz syndrome. *New England Journal of Medicine*, 348(1), 33-40. doi:10.1056/NEJMoa020817

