Study Design	This will be a single site, phase 2, safety and tolerability trial of 4'-phosphopantetheine (4'-PPT), a downstream product of intermediary metabolism in children and adults with pantothenate kinase-associated neurodegeneration (PKAN), an inborn error of vitamin B5 metabolism. There will be two cohorts: For the “ Primary Cohort ”, an initial 6-month, dose-ranging, parallel-group, randomized, double-blind, placebo-controlled phase will be followed by an 18-month, single-dose, open-label phase. During the double-blind phase, participants will be randomly assigned to receive one of three doses (5mg/m ² or 15mg/m ² or 20mg/m ²) or placebo in a 1:1:1:1 distribution. All participants will be assigned to a single dose (15mg/m ²) during the subsequent open-label phase. The primary data analysis will be based on the Primary Cohort dataset. Once the target enrollment of the Primary Cohort is met in the double-blind arm, new participants entering the study will be enrolled directly into an open-label arm that will last until the final subject in the Primary Cohort has completed their participation, including up to 4 additional mos for screening and follow-up. This will be designated the “ Open-label Cohort ”. Because the rolling enrollment into the Open-label Cohort will result in variable duration of participation, the safety and biomarker data from

	
the Open-label Cohort will not be used for the primary data analysis, although a secondary analysis of these data may be used for regulatory filings.
 
The study product will be taken once daily but may be split into divided doses if the participant does not tolerate a single daily dose.
 
Note that the double-blind phase of the study is not intended to be dose-finding: all doses are predicted to be many-fold below toxicity and all doses are predicted to correct the metabolic defect in PKAN, albeit with slightly differing time courses. The range of doses to be used during the double-blind phase is employed purely to test our hypotheses regarding the pharmacodynamic profile of an exploratory 'proof of concept' biomarker, CoASY. The mid-dose of 15mg/m² is based on the minimum effective dose in the mouse and converted to the human equivalent dose using an FDA algorithm and other guidances.

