Primary Outcome	
Our primary endpoints are:
 
 • Safety outcome measures will include treatment-emergent adverse events and abnormalities on standard laboratory tests. TEAE will be collected at 10 time points over 24 months of treatment in the Primary Cohort and collected at up to 7 time points over up to 18 months of treatment in the Open-label Cohort. Laboratory tests will be collected at 9 time points in the Primary Cohort and up to 6 time points in the Open-Label Cohort over the same respective periods. • Tolerability outcomes will be assessed via participant retention in the study and adherence to the study product regimen.
Secondary Outcomes	
Our secondary endpoint is: CoASY mRNA expression levels measured at 8 time points in the Primary Cohort and at up to 6 time points in the the Open-label Cohort.

Safety Assessments	
Treatment-emergent Adverse Events Baseline and at intervals throughout treatment (10 time points for the Primary Cohort and up to 7 timepoints for the Open-label Cohort)
 
 • Treatment-emergent adverse events will be classified according to Medical Dictionary for Regulatory Activities (MedDRA) terminology. • Severity of the AEs will be graded according to the NCI Common Terminology Criteria for Adverse Events, Version 4.0 
Clinical safety laboratory studies Baseline and at intervals throughout treatment (9 time points for Primary Cohort; up to 6 time points for the Open-label Cohort)
 
 • Complete metabolic profile (Includes Na^+, K^+, Cl^-, CO_2, BUN, Creat, Ca^{2+}, Glu, Alb, T. Protein, Alk Phos, T. Bili, AST, ALT) • Complete blood count with auto-differential • Creatine kinase (CK)
Tolerability Assessments	
Participant retention
 
 • During treatment and follow up • Number of participants retained in each arm at each of the follow up time points 
Participant adherence to study product regimen as measure of tolerability
 
 • During treatment and follow up • Mean percent of study product consumed

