Note that the double-blind phase of this study is not intended to be dose-finding: all doses are predicted to be many-fold below toxicity and all doses are predicted to correct the metabolic defect in PKAN, albeit with slightly differing time courses. The range of doses to be used during the double-blind phase is employed to test our hypotheses regarding the pharmacodynamic profile of an exploratory biomarker, CoASY. The mid-dose of 15mg/m² that will be given to all participants during the open-label phase is based on the minimum effective dose in the mouse and converted to the human equivalent dose using an FDA algorithm and other guidances^[13,14]. The actual single daily dose in mL to be taken by the study participant will be calculated by the research pharmacist based on the participant's body surface area. If a subject has difficulty taking the volume of the single dose, then at the Principal Investigator's discretion the dose may be divided into 2 equal volumes and taken twice a day.

7. Study Population

a. Number of Subjects

We will screen up to 150 individuals with the goal of enrolling 64 participants, to achieve 60 participants completing the double-blind arm of the study as the Primary Cohort. We are conservatively allowing for 4 dropouts (5% loss) based on our experience in one other interventional clinical trial with this clinical population; however, if participant loss is higher than anticipated during the projected 24 month recruitment phase, we will strive to replace all dropouts to maximize our chances of achieving 60 participants completing the study. Once enrollment into the Primary Cohort is met, we will shift to enrolling up to 86 additional participants in the direct to open-label arm (Open-label Cohort).

Classic PKAN participants are defined as those with onset of motor symptoms before age 5 and (if over 10 at enrollment) loss of independent ambulation by age 10. Goal is n=30 classic participants.

Atypical PKAN participants are defined as all other PKAN participants who don't meet classic disease criteria. Goal is n=30 atypical participants.

b. Inclusion and Exclusion Criteria

For inclusion in this trial, subjects must:

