Because this clinical trial is being conducted remotely, every effort will be made to ensure that participants complete at least the scheduled safety labs and telephone visits within the study visit windows. A participant-specific schedule of visit dates will be generated at enrollment, and study staff will send visit reminders via phone calls or emails in advance of scheduled blood draws. Per-participant compliance will be closely tracked: participants will not be allowed to complete more than 3 required visits more than 7 days out of window over the life of the study, with a 'required' visit defined as one involving safety lab blood draw and / or adverse event assessment. If compliance drops below this standard during the double-blind phase, the Primary Cohort participant will be terminated from the study, and required to be re-screened and re-randomized as a new participant in order to re-enroll in the study. If compliance drops below this standard during the open-label phase, the study product supply will be suspended but the Primary Cohort or Open-label Cohort participant will still be considered enrolled in the study and ongoing attempts will be made to have the participant complete assessments. If the participant subsequently succeeds in completing the most recent set of missed assessments, study product supply and dosing may be resumed. A repeat episode of non-compliance with the study schedule during the open-label phase will result in the participant's termination from the study. Exceptions may be made on a case-by-case basis, with the input of the medical monitor, DSMB and IRB as needed.

If the participant elects to withdraw from the study prematurely, or if the investigator and / or the participant's medical providers feel it is in the participant's best interests to withdraw from the study early, a Primary Cohort participant will be asked to complete the Month 24 and Month 25 activities and an Open Label participant will be asked to complete the Month 18 and Month 19 activities, if possible. The reason for premature withdrawal will be recorded. Every effort will be made to ensure any remaining study product is returned to the study site.

f. Unscheduled visits

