We will compare the number of participants retained in each arm at each of the follow-up time points [0-(0+1week)-1-3-6-(6M+1week)-7-9-12-18-24-25 months for the Primary Cohort; and 0-(0+1week) -1-3-6-9-12-18-19 for the Open-label Cohort], taking into account whether dropout seems plausibly related to study participation and the mean percent of study product consumed. High retention in the study and product consumption per-protocol will be considered evidence of tolerability.

Analysis of secondary endpoints

We will estimate a CoASY pharmacodynamic profile in response to different doses of the study product in the Per-Protocol dataset. CoASY mRNA expression levels are continuous, measured in normalized differences in cycle times (ΔCt) on the \log_2 scale. Lower ΔCt indicates higher expression levels. We will use regression models controlling for PKAN type to estimate mean levels by treatment arms, including mixed effects when modeling over multiple time points.

To estimate the **change in expression levels after 3±2 days of treatment compared to placebo**, we will use a mixed effects regression model of the form $CoASY_{ijt} = \beta_0 + \beta_{jt}I(group = j)I(time = t \text{ and } t > 0) + \alpha I(cPKAN) + b_i$, $j = \text{placebo, low, mid, high}$; $t = 1$. Each individual contributes two observations (baseline and after); b_i represents the random intercept for subject. Baseline, represented by β_0 , is constrained to be the same for all groups because of randomization. Our primary approach will treat time as binary (0=baseline, 1=treated), though this can later be expanded to capture differences between days 1-5 of treatment. The β_{jt} represent mean changes from baseline for the three dose groups and placebo. An indicator for PKAN type (cPKAN or aPKAN) is included to reflect its role in stratified randomization. We will review regression coefficients as estimates of the magnitude of effect and test $\beta_{\text{placebo}1} - (\beta_{\text{low}1} + \beta_{\text{mid}1} + \beta_{\text{high}1})/3 = 0$ with a two-sided alpha of 0.1 to determine whether CoASY mRNA expression levels rose in all the study product-treated participants after initiation of treatment compared to placebo.

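### A switch to divided dosing registers in neither tolerability measure, and no count of switches by arm is planned

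*Combined protocol and SAP*

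**What the plan says.** The synopsis (Primary Outcome) and section 2 state that tolerability "outcomes will be assessed via participant retention in the study and adherence to the study product regimen". The synopsis entry on Tolerability Assessments gives the adherence summary as "Mean percent of study product consumed", and section 10.d defines the ratio: "Adherence to the study product regimen will be assessed by calculating actual product consumed / expected product consumption". The Tolerability Analysis, in both the synopsis and section 10.b, adds the reading rule: "High retention in the study and product consumption per-protocol will be considered evidence of tolerability".

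Divided dosing is described twice. The synopsis (Study Design) says the product "may be split into divided doses if the participant does not tolerate a single daily dose". Section 6 gives a different trigger, "If a subject has difficulty taking the volume of the single dose", makes the decision one for the Principal Investigator, and says that "the dose may be divided into 2 equal volumes and taken twice a day".

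For adverse events, the Safety Analysis (synopsis and section 10.b) lists any change made to the study product because of the event among the details to be collected. Section 8.e deals with open-label participants who fall below the visit-compliance standard, and says of them: "the study product supply will be suspended but the Primary Cohort or Open-label Cohort participant will still be considered enrolled in the study".

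**The concern.** The synopsis describes a participant who does not tolerate the regimen as assigned and provides a way to keep that participant on product. After the switch the participant is still enrolled and can take the full daily amount, so both tolerability measures count the case in the product's favour.

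This matters because the primary hypothesis is that safety and tolerability do not differ to a clinically significant degree between active and placebo. An insensitive measure favours that hypothesis. With about 15 evaluable participants per arm and group differences judged clinically rather than by test, the reviewing physician can weigh only what the tables and listings show. If one arm needed divided dosing more often than another, that would bear directly on tolerability, and the tolerability tables would not show it.

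**Working it through.** The plan states no figure for this point, so there is nothing to reproduce. The check applies the plan's own definitions to a participant who switches.

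**Retention.** Section 10.d describes exit as loss to follow-up or no longer being willing or able to participate. A switch is neither, so the participant is counted as retained.

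**Adherence after the switch.** Let V be the assigned daily volume. Section 6 divides it into two equal parts, so consumption is V/2 + V/2 = V. Expected consumption is also V, and the ratio is V/V = 100% if all of it is taken. The number of administrations per day does not enter the formula.

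**Adherence including doses missed before the switch.** Assume a double-blind phase of 183 days, k days fully missed before the switch, full intake otherwise, and period weights proportional to period length. Adherence = (183 − k)/183.

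| Missed days k | Adherence |
|---|---|
| 0 | 100% |
| 3 | 98.4% |
| 7 | 96.2% |
| 14 | 92.3% |
| 45 | 75.4% |
| 46 | 74.9% |

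A participant would have to miss 46 days before falling below the 75% consumption that defines the Per-Protocol dataset.

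**Arm mean.** With 15 per arm and m participants switching, mean adherence = 100 − 100 × (m/15) × (k/183), everyone else being at 100%.

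| Switching, m of 15 | k = 0 | k = 7 | k = 14 |
|---|---|---|---|
| 0 | 100% | 100% | 100% |
| 5 | 100% | 98.7% | 97.4% |
| 15 | 100% | 96.2% | 92.3% |

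The measure responds only to missed product. If little is missed, an arm in which nobody switched and an arm in which everybody switched look the same or nearly so.

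**Other places a switch might appear.** The adverse-event record holds product changes made because of an event, so it covers a split only when an adverse event was captured. Difficulty with volume, the section 6 trigger, need not be one. Section 10.d also plans individual listings of safety and tolerability events, but it does not name switches to divided dosing. No section tabulates switches by arm.

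**The case against.** The strongest reply is that intolerance with symptoms already has a route into the primary analysis. Treatment-emergent adverse events are a primary endpoint, they are summarised by arm, product changes are recorded with them, and a blinded physician reviews group differences. On this view the uncounted cases are splits for volume or taste, in participants who go on to take the full daily amount. Retention with adherence is also a recognisable definition of tolerability. Much of this stands. The gap is in the tolerability measures, not in all the safety data. It does not close the gap: a split without a captured adverse event is summarised nowhere, and a split with one is only a detail of that event.

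Four stronger readings are tempting, and the documents do not support them.

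- *The protocol expects intolerance.* It makes provision for it, but predicts very low toxicity.
- *Anyone who switches scores as fully adherent.* Doses missed around the switch or later still lower the percentage.
- *A dose-related difference is being hidden.* At the stated 1 mg/mL the active doses correspond to 5, 15 and 20 mL per m², a four-fold range, so a gradient in splitting is plausible. However, the documents do not give the placebo volume or say whether volumes are matched for blinding, and they give no splitting rate.
- *Suspension of supply distorts the active-versus-placebo comparison.* The suspension in section 8.e follows missed visit windows, not intolerance, and applies only in the open-label phase. In the double-blind phase the same non-compliance leads to termination.

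**Conclusion.** The concern holds as a gap in measurement. Neither retention nor percent consumed registers a switch to divided dosing, and the stated reading rule then treats the participant as evidence of tolerability. Splits tied to a captured adverse event can be found in the safety data; other splits appear in no planned summary. No count by arm exists for either kind.

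The true size is unknown, because the documents give no switching rate. The percentages above rest on an assumed 183-day phase and assumed numbers of missed days and switchers. They show that the measure is insensitive, not that intolerance will occur or differ between arms. That retention or adherence follows from the definitions does not depend on those assumptions.

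A secondary point concerns the open-label phase alone: because a participant without supply still counts as enrolled, the number retained can exceed the number on product. Section 10.d does not say whether expected consumption continues to accrue during a suspension.

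The change is worth making because tolerability is in the primary objective and the remedy is small.

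**What to change.** 1. Record the date and reason for each switch from single to divided dosing, whether or not an adverse event is reported.
2. Add to the Tolerability Analysis, in both the synopsis and section 10.b, the number and percentage of participants switched: by arm for months 0–6, and by initial arm for the open-label phase. Show these beside retention and adherence.
3. Amend the reading rule so that these counts are considered before high retention and consumption are taken as evidence of tolerability.
4. Reconcile the triggers for splitting in the synopsis and section 6, so that the recorded reasons have one meaning. Which trigger applies is for the study team to decide.
5. For the open-label phase, show the number on product beside the number retained at each time point.

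None of this changes a dose or a clinical rule. The cost should be about one data field plus analysis wording. Section 6 already makes the split a decision of the Principal Investigator, so there is a natural moment to record it, although the case report forms and diary fields are not in these documents and the cost cannot be confirmed from them. The downside is that the tolerability picture may look slightly less favourable.
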